1.2 Literature Review

This literature includes a variety of workplace and laboratory studies assessing performance of PAPRs worn by test subjects. Unlike the U.S. NIOSH respirator certification standard (42 CFR 84) which specifies minimum flowrates allowable for PAPRs, British EN standards have no such requirement of lower limitations (British Standards Institute (a, b), 2008); thus studies of British EN certified PAPRs are included in this literature review, to provide reference for safe and feasible modification of a device to a lower than NIOSH minimum flow rate. This protocol will involve human subject testing with PAPR flow rates below the current NIOSH minimum requirements. Studies that used a supplied air respirator (SAR) are included in this review if flow rates were stated and judged to be within the range of a typical PAPR (170 to about 250 L/min).

Da Roza et al completed one important laboratory study which examined the effects of work rate, blower airflow, and beard growth on penetration of the polyethylene glycol 400 test aerosol in relation to the performance of a tight-fitting half facepiece PAPR and two LFF PAPRs, each fitted with HEPA filters (Da Roza et al., 1990). The half-mask PAPR was varied in flow from 225 to 114 Lpm; the two LLF PAPRs had their flow varied from 170 to 86 Lpm and 202 to 114 Lpm. Airflow and differential pressure within the device were measured while the subjects walked on a graded treadmill at gradually increasing work rates. At 80% of each subject's maximum work rate, PAPR airflow rates were varied from those produced by fully charged batteries to rates below the required NIOSH minimum. After four to six minutes' cool-down, additional measurements were taken while subjects performed the following exercises for two minutes each: Bending and squatting, running in place, touching toes, raising arms over head, holding a rod while twisting torso and raising arms, and normal breathing. Each test was conducted with the subject clean-shaven, with three days beard growth, and again after 2-3 months of beard growth. Representative raw penetration data were presented rather than calculated laboratory protection factors. The authors found increasing work rate elevated penetration for both LFFs but did not increase penetration for the tight-fitting PAPR on cleanshaven subjects. Similar results were suggested for varying each device's airflow rates. Beard growth increased penetration of the tight-fitting PAPR, but the effect was not seen with the LFF devices. Negative pressure was seen within all the devices under some of the test conditions. Given the conflicting evidence for particle penetration in this study, further research is warranted for flow rate and work rate effect on PAPR performance.

Clayton et al. (2002) measured SWPF laboratory performance of two full facepiece PAPRs approved under European performance criteria (BSI, 1992). Limitations included failure to fit test the subjects, protrusion of spectacle temple bars through the face seal, and simulated battery failures, and lack of work rate or flow rate reported outcomes. The authors continuously measured facepiece penetration of a sulfur hexafluoride (SF $_6$) challenge over 3-4 hours of simulated asbestos removal. Work rate was not reported, but the tasks described would likely be classified as moderately heavy work. Neither airflow to the facepiece nor facepiece pressure was

monitored during the tests. Overall reported SWPF values ranged from 2,000 to 20,000 over 20 simulations. The remaining simulation had a SWPF of 400. Our current protocol also incorporates full-facepiece PAPRs to compare their performance to PAPRs with loose-fitting hoods/facepieces, and the design will remove the limitations experienced during this trial.

Seiple and Pappas (2003) tested the 3M Breathe Easy PAPR with a butyl rubber hood in a SWPF study. The challenge agent was 20-40 mg/m³ polydisperse corn oil with a mass median aerodynamic diameter (MMAD) of 0.4-0.6 µm. Laser photometry was used to measure challenge aerosol and penetration on the operating (blower on) PAPR. U.S. Army standard sampling probes were used to collect in-hood samples. Seven standard fit testing exercises plus "sight the rifle," "reach for the floor and ceiling," and "on hands and knees, look left and right" were performed for one minute each by 24 test subjects. All SWPFs were greater than 20,000. Our current protocol also employs a varied set of dynamic exercises to determine the effect of each exercise on particle penetration in the PAPR hood or facepiece, however additionally studies flow rate effects.

Cohen et al. conducted a large SWPF study of loose fitting PAPRs with HEPA filters and supplied air respirators used in the pharmaceutical industry (Cohen et al., 2001). Five PAPRs with hoods, one loose-fitting facepiece PAPR, and six hood-style SARs were tested. Seventeen volunteers (60% men, 40% women) wore the devices in a test chamber. A polyethylene glycol 400 aerosol at a concentration of approximately 17 mg/m³ and a mass median diameter of 0.44 μm was used as the challenge atmosphere. Light-scattering photometry was used to measure C₀ and C_i aerosols; the C_i sample was taken with a nasal cannula beneath the subject's nose. The exercise regimen included 12 two-minute exercises that included "raising arm above head," "twisting at the waist while holding rod and raising and lowering arms," "scooping of pebbles," and "building of concrete block wall" in addition to standard fit testing exercises. Airflow from the PAPR blower or air supply and differential pressure inside the respirator were measured continuously during each test. Lower fifth percentile SWPFs for the five PAPRs ranged from 150,000 to >250,000, defined as the limit of quantification for the experimental setup. Supplied air devices had fifth percentile SWPFs ranging from 86,000 to >250,000, except for one SAR. The fifth percentiles for this device were < 20: the authors attributed this poor performance to an apparent design flaw: The device did not have a bib to tuck into the wearer's clothing. Fifth percentiles for the same device with a bib were four orders of magnitude higher. Additional insights can be gained from the airflow and differential pressure measurements Cohen et al. reported. Mean air flow rates in their study were all above the NIOSH required minimum of 170 L/min, ranging from 176 to 304 L/min. The poorly performing SAR had a mean flow rate of 234 L/min and a minimum of 203 L/min. One hood-style PAPR and the LFF PAPR, were found to have occasional airflow measurements as low as 132 and 149 L/min, respectively. Interestingly, the hood-style PAPR had slightly higher fifth percentile SWPFs. The authors noted "There was no consistent pattern among the relationship of pressure measurements taken inside the facepiece [sic] and the corresponding SWPFs recorded." The Cohen et al. study appears to support the ideas suggested later by several studies conducted by Johnson and Koh (Johnson et al., 2008; Koh et al, 2011; Johnson et al., 2011; Koh and Johnson, 2012). That is, design characteristics may affect the protective performance of loose-fitting devices in addition to their rate of airflow, and higher flow rates do not assure a higher level of performance. The effect of occasional negative pressure spikes on the protection provided by loose-fitting respirators is not great; this could be related to dead volume, e.g., hood vs. LFF. Our current protocol design includes a diverse selection of PAPR designs to determine if the overall type of design (e.g., helmet

113

114

115116

117118

119120

121

122

123

124

125

126

127

128129

130 131

132

133 134

135

136137

138

139 140

141

142

143

144

145146

147

148

149

150

151

152153

154

155156

157158

159

160

mounted blower vs. belt-mounted blower, full shroud vs. loose-fitting facepiece at chin, the use of a tight-fitting full-facepiece) affects particle penetration. In addition to including a diverse selection of PAPR designs, our protocol will also study the effects of subject work rate, PAPR flow rate, and type of exercise on PAPR performance.

1.3 Current State of Knowledge

Previous laboratory studies are inconclusive regarding the effects of flow rate and work rate on simulated protection, likely due to various limitations identified in their protocols, supporting additional research is warranted. Da Roza et al. (1990) concluded no increase in penetration with increasing work rate for a tight-fitting PAPR but did however note an increase with two LFF models. Bolsover et al. (2006) also found increased penetration with decreased flow rate in a single LFF. Conversely, the Cohen et al. study (2001) demonstrates that some negative pressure events (due to increased work rate or decreased airflow) do not significantly affect SWPFs. The work of Johnson and Koh further suggest that design considerations such as shrouds, dead volume and a tortuous path of leaked air to the breathing zone may also contribute to how much contaminated air reaches the respiratory tract (Johnson et al., 2008; Koh et al, 2011; Johnson et al., 2011; Koh and Johnson, 2012).

Additional research is necessary to fully understand how LFF PAPRs provide protection to the user. The literature suggests that if changes are made to PAPR certification requirements, they should be performance oriented. That is, a PAPR must demonstrate the ability to reduce exposure by a specified amount rather than deliver, for example, a specified airflow. Ideally, laboratory performance requirements would be validated with workplace test methods before they are implemented.

2.0 OBJECTIVES AND SPECIFIC AIMS

PAPRs have become an important and attractive type of respiratory protection to defend against high-level respiratory hazards and infectious body fluids in health care settings. But challenges (noise, overall bulkiness, visual impairment, interference with tasks, and issues related to decontamination, among other problems associated with their use) have limited widespread utilization of PAPRs in healthcare settings. This is because PAPRs were originally developed to protect industrial workers (primarily in mining) with heavy work rates. And the designed flow rate of PAPRs is driven by the work rate of users. Since the typical work rates of healthcare workers are significantly lower than those of industrial workers, a lower PAPR air flow rate may be justified to provide a sufficient level of protection. This study will determine whether protection is maintained at lower flows during simulated workplace exercises.

The objectives in this study, including studying the effect of PAPR flow rate, will aid the development of PAPRs, in three ways; 1) offering alternative respiratory protection in the event of a filtering facepiece respirator (FFR) shortage, 2) standards development, and 3) allowing for the development of next generation PAPRs.

2.1 Primary Objectives

- a. Understand the relationship between PAPR flow rate and SWPF during routine healthcare exercises
- b. Understand the relationship between user work rate and PAPR SWPF

2.2 Secondary Objectives

- a. Assess PAPR usability and comfortability at varying work and flow rate conditions
- b. Understand the relationship between PAPR RIC design and SWPF

2.3 Exploratory Objectives

- a. Develop and evaluate next generation PAPR prototypes using SWPF test methods
- b. Evaluate the SWPF test method as a standardized test method for PAPRs with a loose-fitting facepiece

[figure not shown]
3.0 STUDY DESIGN AND METHODS

This project promotes developed PAPR design through 1) improved test methods for quantifying PAPR performance and usability, 2) better understanding of the relationships between flow rate, work rate, design characteristics, and performance. The multi-disciplinary project team includes collaborators from across NPPTL. The key scientific questions this study will address include the relationships between flow rate and protection as well as work rate and protection. The interaction of design features such as dead volume and the size/configuration of shrouds will also be studied. The answers to these questions will impact potential solutions to make PAPRs quieter and lighter to improve use in a healthcare setting. The information will also guide decisions regarding potential changes to the PAPR standard 42 CFR 84 and OSHA standard 29 CFR Parts 1910, 1915, and 1926. The design of this study includes three phases to be completed in sequential order (Figure 1.).

Figure 1. SPARTAN Protocol Flow Chart (CONSORT 2010)

3.1 Screening Design

A sample of 25 evaluable test subjects will be included in this study and up to 75 subjects enrolled. Following recruitment and consent, subjects will undergo facial measurements to determine if they fit into an available cell category of the NIOSH/NPPTL Bivariate Panel (Fig. 2 and Table 2) used to collect facial dimension representation of the US workforce. The sample size of 25 subjects was first proposed by Landsittel et al. (2014) and later supported by interpanel variability results reported by Zhuang et al. (2015) and Liu et al. (2016). The numbers in each cell in Figure 2 represent cell category number. The numbers in parentheses indicate the number of subjects to be sampled in that category. When the subject's face length or face width fall on the boundaries, the subject is classified into the higher number cell category.

A sample size of 25 subjects (calculated using G*Power 3.1.9.2.) also provides the researchers with acceptable levels of precision to estimate population parameters and to compare SWPF results across flow rates and work rates. Previous research by the PI has found the standard deviation among sets of SWPF scores for PAPRs to be considerably low when compared to the average. Studies have shown a geometric standard deviation of ~1.5-3.5—while SWPF mean values can be in the thousands. This mean to standard deviation ratio allows for very precise estimates of population parameters with relatively small samples of 25 subjects. It also makes comparison among conditions of the study to be precise. However given that small differences in

SWPF can make a meaningful practical difference the researchers' goal is to estimate precise population parameters and detect small differences between conditions as significant. A sample of 25 and a repeated measures design (as explained below) allow the researchers to detect an effect size of 0.4 as significant. This effect size means that a little less than one half of the standard deviation can be detected as significant when dependent means are compared.

After being determined to fit into an available cell category, thus filling the target population of the U.S. workforce, the remaining screening components assess the subjects' abilities to wear a respirator and perform the required exercises safely. The medical screening components seek a subject population without chronic health problems that may increase the risk when exercising or wearing a respirator. These risk factors may be self-reported by the subjects or physiologically measured.

Subjects will complete the OSHA/NPPTL Medical Evaluation form (Appendix D), the NPPTL Screening Medical Evaluation (Appendix E), and the NPPTL Subject Data Form (Appendix F). Subjects that would like to participate in more than one Phase of this study, which may lead to > one year involvement, will be re consented and re-screened at minimum yearly, as is standard in human subject's research, for collection of potential baseline result changes, for example facial dimension, weight, and maximal heart rate. Because OSHA has determined that fit testing of respirators must be completed annually at minimum due to potential changes in baseline measurements and medical considerations, we will use their suggested length of time determined by OSHA research and expertise in this arena, to base our re-screening timeframe, in the event a subject participates for > one year. Additionally, a yearly medical evaluation has been established in the NPPTL Protocol for Human Subject Testing for Respirator Inward Leakage (IL) (HSRB 14-NPPTL-02).

However, we will additionally at every study visit during each calendar year review changes in health and wellbeing with subjects prior to testing, to also reduce risk in between re-screening each year. If during a routine visit within a calendar year from date of screening, a subject is found to have medical and/or physical changes from baseline that may increase their risk to participate (based on Pre Visit Medical Evaluation with the medical monitor CRNP), consideration for early re-screening or participant discontinuation will be reviewed by medical monitor CRNP and study team.

Figure 2. NIOSH panel based on face length and face width

Face Width (mm)

	138.5	120.5	134 132.5	4.5 144	146.5 4.5	158	3.5
	128.5	6 (2)		9 (2)		10 (2)	
th (mm	118.5	6 (2)	·	7 (4)		8 (2)	
Face Length (mm)	108.5	3 (2)		4 (5)		5 (2)	
Fac	98.5	1 (2)		2 (2)		U (2)	

Table 2. Percentage of Population and Number of Subjects by Cell for the Panel

NIOSH BV Cell	Percentage of Population	No. of Test Subjects
1	5.5	2
2	5.3	2
3	10.5	2
4	25.0	5
5	7.1	2
6	5.7	2
7	21.3	4
8	8.7	2
9	5.2	2
10	3.5	2
Total	97.7	25

Fit Testing

Tight fitting PAPR models require an approved OSHA fit test to determine safe and protective seal for the user. To verify NIOSH/NPPTL cell category allocation accuracy, each subject will complete fit testing for all three tight fitting PAPRs to be used in Phase II of this study, even if a subject is anticipated to only participate in Phase I. For the tight-fitting PAPR fit tests, a 2% NaCl solution in distilled water will be used as a generator solution under room conditions (in a laboratory, but outside of a test chamber). A particle generator (Model 8026, TSI, Shoreview, MN) and an OSHA approved condensation nuclei count protocol with PortaCount Plus (Model 8038; TSI) will be used.

Maximal Graded Exercise Test (GXT)

Subjects will undergo a Maximal Graded Exercise Test according to the Bruce protocol (Appendix K) to further review medical eligibility and subject specific termination criteria, such as maximal heart rate, for this study. This test will also obtain physiological measurements

(maximal oxygen uptake and maximal heart rate) that will be used in Phase I calculations. This will take place in the NPPTL physiology lab using a treadmill and metabolic cart. It may also take place in the NPPTL Building 40 environmental test chamber and high bay area, which is also equipped with a treadmill and metabolic cart. See Appendix K for complete procedure and metabolic cart measurements.

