3.2 Phase I

Phase I is designed to test a novel healthcare practice-based exercise regimen for SWPF testing of PAPRs with 25 evaluable subjects that represent the US workforce facial measurements. In this phase, subjects will not wear PAPRs, however they will complete one 30-minute regimen that includes ten, 3-minute exercises to determine Work Rate category allocation per exercise. The simulated workplace exercises were created based on: a) exercises from ANSI (American National Standards Institute) and OSHA respirator test protocols (ANSI, 2010; CFR, 1998); and b) routine healthcare activities (Table 3.). This phase will be completed without PAPRs and subjects will have physiological measurements taken with a metabolic cart. During each exercise regimen replicate subjects will be equipped with a heart rate (HR) monitor and siliconerubber oronasal facemask from the metabolic cart. Expired air sample will be analyzed for oxygen uptake (VO₂), minute ventilation (V_e), and carbon dioxide (VCO₂).

25 subjects x 1 regimen x 3 replicates = 75 max oxygen uptake (VO₂) and 75 max heart rate (HR) values per exercise to determine work rate category allocation (Table 4.). In this study phase, the data will be analyzed after all 25 subjects complete the first of three attempts so that each exercise will have 25 values calculated. Subjects will complete all consent and screening items, along with the first replicate of Phase I during their first visit (~3 hours) and will complete the second and third replicates on a different visit (~3 hours). Phase I will be conducted in conjunction with screening and completed over 2 visits (~6 hours total). It is anticipated that all subjects will complete Phase I/screening in 3-6 months (July 2019-December 2019).

Mean Population Parameter with 95% (1.960) confidence interval will be used to analyze data. For each exercise, if the 95% confidence interval is within theoretical bounds for each work rate, then the second and third replicates will not need to be completed and Phase II of this study will begin. The theoretical bounds can be found under the relative intensity columns in Table 4.

Hypothesized Work Rates

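### Section 3.1 misuses the geometric SD to argue precision, and its claim that 25 subjects detect an effect size of 0.4 cannot be reproduced from the protocol

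*Protocol*

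**What the plan says.** Section 3.1 takes 25 subjects first from the facial-size panel and its supporting studies, then adds a statistical case: "A sample size of 25 subjects (calculated using G*Power 3.1.9.2.) also provides the researchers with acceptable levels of precision".

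The precision part of that case runs: "Studies have shown a geometric standard deviation of ~1.5-3.5—while SWPF mean values can be in the thousands". From this it concludes: "This mean to standard deviation ratio allows for very precise estimates of population parameters with relatively small samples of 25 subjects".

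The power part reads: "A sample of 25 and a repeated measures design (as explained below) allow the researchers to detect an effect size of 0.4 as significant". The protocol explains this as meaning that "a little less than one half of the standard deviation can be detected as significant when dependent means are compared".

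The section promises an explanation further on, but no calculation follows. Section 3.3 describes 8 models, 2 flow rates and 2 replicates per subject, analysed by three-way repeated measures ANOVA. Section 8.2 puts the analysis on log SWPF. Sections 8.2 and 8.3 plan a power analysis only after the first replicate. The one error level stated anywhere is the 95% interval for Phase I.

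**The concern.** **Precision.** A GSD multiplies and divides; it has no SWPF units. Placing 1.5 to 3.5 next to a mean in the thousands makes the spread look negligible, but the two numbers are not on the same scale. The objection holds whether the mean is arithmetic or geometric (the protocol does not say which). It also conflicts with section 8.2, which uses the geometric mean and GSD properly.

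**Detectable effect.** The protocol's own gloss describes a comparison of two dependent means with a standardised difference of 0.4. On the most direct reading, 25 pairs are too few for conventional power at that size.

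**Stake.** Section 2.0 asks whether protection is maintained at lower flow, and section 3.0 says the results will guide possible changes to respirator standards. If readers believe small differences are detectable, a non-significant flow or work-rate contrast is easily taken as evidence that protection is unchanged.

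**Working it through.** **Inputs from the protocol.** n = 25; effect size 0.4; dependent means; GSD 1.5 to 3.5; 8 models × 2 flow rates × 2 replicates; log scale (sections 3.1, 3.3, 8.2).

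**Assumed, because not stated.** Alpha 0.05; 80% power as benchmark; one- and two-sided tests both tried; within-subject correlation ρ varied.

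**Reproducing the plan's figure.** This is not possible: alpha, sidedness, power, ρ and the effect index are all missing. The steps below cover the readings the text allows.

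**1. What the GSD implies.** On the log scale the SD is s = ln(GSD), so s = 0.405 (GSD 1.5) to 1.253 (GSD 3.5).
- Coefficient of variation of a lognormal variable = √(exp(s²) − 1): **42%** to **195%**.
- 95% CI factor for a geometric mean = exp(2.064 × s / √25): exp(0.167) = **1.18** to exp(0.517) = **1.68**.

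**2. One paired comparison, 0.4 SD of the differences.** Noncentral t, 24 df, noncentrality 0.4 × √25 = 2.00.
- Power 48.4% two-sided, 61.7% one-sided.
- Effect for 80% power at n = 25: 0.58 SD two-sided (0.51 one-sided).
- n for 80% power at 0.4 SD: 52 two-sided (41 one-sided).

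**3. One paired comparison, 0.4 SD of single values.** The standardised difference is 0.4 / √(2(1 − ρ)).

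| ρ | Two-sided power |
|---|---|
| 0 | 27% |
| 0.3 | 37% |
| 0.5 | 48% |
| 0.7 | 70% |
| 0.8 | 86% |

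For 80% power, 0.4 / √(2(1 − ρ)) = 0.584, so ρ = 1 − (0.4/0.584)²/2 ≈ 0.77.

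**4. Phase II flow effect pooled over 8 models, one replicate.** Take 0.4 SD of a single value, with no subject main-effect variance and a share τ² of the total variance due to subject-by-flow variation. The variance of a subject's mean difference is 2[τ² + (1 − τ²)/8].
- τ² = 0: variance 0.25, standardised difference 0.80, power 97%.
- τ² = 0.10: variance 0.425, standardised difference 0.61, power 84%.
- τ² = 0.20: variance 0.60, standardised difference 0.52, power 70%.

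**5. Detectable fall in SWPF for one paired comparison at 80% power.** Fall = 1 − exp(−0.584 × s × √(2(1 − ρ))).

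| ρ | GSD 1.5 | GSD 3.5 |
|---|---|---|
| 0 | 28% | 64% |
| 0.5 | 21% | 52% |
| 0.8 | 14% | 37% |

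At ρ = 0.5 the SD of the paired log difference equals ln(GSD).

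**The case against.** A reader might infer from step 2 that the trial as designed has only about 48% power. The documents do not support that. The sentence credits the repeated measures design as well as the sample size, and that design gives each subject many values per flow rate. Step 4 shows that the pooled flow effect could be well above 80%, or below it, depending on a variance component the protocol does not give.

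The SD is also unspecified. The only one section 3.1 describes is the spread among SWPF scores, which suggests single values rather than differences; power then depends on ρ.

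A reader might also infer that an observed effect of 0.4 could never be significant, since t = 0.4 × √25 = 2.00 falls short of 2.064 (p = 0.057). That holds only two-sided and in SDs of the differences. One-sided, p is 0.028. In SDs of single values, the result is significant two-sided once ρ exceeds about 0.53.

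It may be tempting to suppose that 0.4 was entered in G*Power as Cohen's f, which for two conditions equals a difference of 0.8 SD. Nothing in the protocol says so.

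Finally, 25 rests first on the facial panel, and a later power analysis is planned. Both are true, so the number itself is not in question. Neither corrects the two statements in section 3.1. Pooling over models also does not help contrasts within one model, and respirator design is a secondary objective.

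**Conclusion.** The precision argument is wrong as written, and that conclusion needs no assumption about power. A GSD of 1.5 to 3.5 is a coefficient of variation of about 42% to 195% under lognormality, which is not low variability. The geometric mean is estimated to within ×/÷1.18 to ×/÷1.68 at 95% confidence.

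The 0.4 claim is irreproducible rather than shown to be false. On the direct reading (one two-sided 5% paired comparison, SD of the differences), power is about 48%, and 0.58 SD is needed for 80%. In SDs of single values, the claim reaches 80% power only with ρ of about 0.77 or more. These figures apply to a single paired contrast under the stated assumptions. They are not the power of the whole design, and the pooled flow effect is left open.

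**What to change.** Keep n = 25. In section 3.1:

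1. Delete the mean-to-SD argument. Give precision as 95% CI factors on the geometric mean: ×/÷1.18 (GSD 1.5) to ×/÷1.68 (GSD 3.5).
2. Replace the 0.4 sentence with:

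> For a single paired comparison of log SWPF in 25 subjects, two-sided alpha 0.05, 80% power is reached for 0.58 SD of the paired log difference. If that SD equals ln(GSD) (within-subject correlation 0.5), this is a 21% (GSD 1.5) to 52% (GSD 3.5) reduction in geometric mean SWPF; for correlations of 0 to 0.8 the range is 28%–14% and 64%–37%.

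3. State separately any power claimed for the pooled flow or work-rate main effect, with the variance components it assumes, including subject-by-flow (or subject-by-work-rate) variance.

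The cost is wording only, with no change to enrolment, visits or analysis. The drawback is that the stated detectable effect becomes less favourable.
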